10.1.3. Financial Disclosure

Include text related to financial disclosure if not included in another document.

Investigators and sub-investigators will provide the sponsor with sufficient, accurate financial information as requested to allow the sponsor to submit complete and accurate financial certification or disclosure statements to the appropriate regulatory authorities. Investigators are responsible for providing information on financial interests during the course of the study and for 1 year after completion of the study.

10.1.4. Informed Consent Process

Written informed consent will be obtained prior to conducting any study-related procedures.

Participants must be informed that their participation is voluntary. The principal investigator or designee will explain the study to the participant or his/her legally authorized representative and answer all questions regarding the study. The principal investigator or designee will conduct the consent discussions on an individual basis with each participant. Adequate time will be allowed for all questions to be addressed. Potential participants will be interviewed to ensure that they meet all entry criteria relating to history.

10.1.5. Informed Consent Forms

Informed consent for study participation

Participants will be required to sign a statement of informed consent that meets the requirements of 21 Code of Federal Regulations (CFR) 50, local regulations, ICH guidelines, Health Insurance Portability and Accountability Act (HIPAA) requirements, where applicable, and the IRB/IEC or study center. The informed consent will be obtained by the use of a written consent form approved by the IRB or IEC.

Consent for HIV testing will also be obtained prior to enrollment.

Other consents will be presented to the participant which are optional and if not signed, would not exclude the participant from the study:

- consent to collect, store and testing of samples for research not described in the protocol;
- consent to allow any remaining specimens originally taken for mandatory testing to be used for research not described in the protocol
- consent to genetic testing.

Sample testing will be in line with the consent of the participant.

A copy of the signed consent forms shall be given to the participant prior to conducting any study-related procedures.

The medical record must include a statement that written informed consent was obtained before the participant was enrolled in the study and the date the written consent was obtained. The authorized person obtaining the informed consent must also sign the ICF.

If there is a change to the ICF during the conduct of the study, participants must be re-consented to the most current version of the ICF.

Any withdrawal of consent for sample testing will be documented in the eCRF.

Laboratory assays for primary and secondary endpoints will be carried out in South Africa. Participants will be informed that some of the assays for exploratory endpoints may be carried out in laboratories outside South Africa. If participants will be asked to consent to optional exploratory research using the remainder of mandatory samples, include text that addresses the use of remaining mandatory samples for optional exploratory research.

Participants will be told that they are free to refuse to participate and may withdraw their consent at any time and for any reason during the storage period.

10.1.6. Data Protection

Participants will be assigned a unique identifier by the sponsor. Any participant record or dataset that is transferred to the sponsor will contain the identifier only; participant names or any information which would make the participant identifiable will not be transferred to the sponsor.

The participant must be informed that his/her study-related data will be used by the sponsor in accordance with local data protection law. The level of data disclosure must also be explained to the participant.

The participant must be informed that his/her medical records may be examined by Clinical Quality Assurance auditors or other authorized personnel appointed by the sponsor, by appropriate IRB/IEC members, and by inspectors from regulatory authorities.

10.1.7. Dissemination of Clinical Study Data

Study information from this protocol will be posted on publicly available clinical trials registers (clinicaltrials.gov and the South African registry) before enrolment of participants begins.

The final study report will include all available safety data, clinical assessments, and concomitant medications through the final study visit. The database will be locked prior to unmasking and preparation of the final study report when all of the above data have been

entered, reviewed, and all queries related to the data have been addressed. Modifications or additions to the analyses will be included in the relevant SAP. Any decisions to deviate from the planned analyses described in the protocol and in the SAP will be described in detail in the final study report.

The final clinical study report will be reviewed and approved by the sponsor signatory and the principal investigator.

Summaries of the results of the study will also be posted on the same websites.

10.1.8. Data Quality Assurance

All participant data relating to the study will be recorded on printed or electronic CRF using an Electronic Data Capture (EDC) system, unless transmitted to the sponsor or designee electronically (e.g., laboratory data). The investigator is responsible for verifying that data entries are accurate and correct by physically or electronically signing the CRF.

The investigator must maintain accurate documentation (Appendix 1, Section 10.1.9) that supports the information entered in the CRF.

The study will be monitored regularly by the sponsor or its designee throughout the study period. The investigator must permit study-related monitoring, audits, IRB/IEC review, and regulatory agency inspections and provide direct access to source data documents.

Monitoring details describing strategy (e.g., risk-based initiatives in operations and quality such as Risk Management and Mitigation Strategies and Analytical Risk-Based Monitoring), methods, responsibilities and requirements, including handling of noncompliance issues and monitoring techniques (central, remote, or on-site monitoring) are provided in the Monitoring Plan.

The sponsor or designee is responsible for the data management of this study including quality checking of the data.

The sponsor assumes accountability for actions delegated to other individuals (e.g., Contract Research Organizations).

Study monitors will perform ongoing source data verification to confirm that data entered into the CRF by authorized site personnel are accurate, complete, and verifiable from source documents; that the safety and rights of participants are being protected; and that the study is being conducted in accordance with the currently approved protocol and any other study agreements, ICH GCP, and all applicable regulatory requirements.

Records and documents, including signed ICFs, pertaining to the conduct of this study must be retained by the investigator for 15 years after study completion unless local regulations or institutional policies require a longer retention period. No records may be destroyed during the retention period without the written approval of the sponsor. No records may be transferred to another location or party without written notification to the sponsor.

10.1.9. Source Documents

Source documentation consists of existing medical records and/or study records developed and maintained by the investigator. Source documents provide evidence for the existence of the participant and substantiate the integrity of the data collected.

Data recorded on source documents will be transcribed onto case report forms (CRFs) or entered using electronic case report forms (eCRFs) using an EDC system.

Data entered in the eCRF that are transcribed from source documents must be consistent with the source documents or the discrepancies must be explained. The investigator may need to request previous medical records or transfer records, depending on the study.

For the purpose of monitoring and auditing the study, source documentation will consist of existing medical records and/or study records developed and maintained by the investigator.

10.1.10. Study and Site Closure

The sponsor designee reserves the right to close the study site(s) or terminate the study at any time for any reason at the sole discretion of the sponsor. Study sites will be closed upon study completion. A study site is considered closed when all required documents and study supplies have been collected and a study-site closure visit has been performed.

The investigator may initiate study-site closure at any time, provided there is reasonable cause and sufficient notice is given in advance of the intended termination.

Reasons for the early closure of a study site by the sponsor or investigator may include but are not limited to:

- Failure of the investigator to comply with the protocol, the requirements of the IRB/IEC or local health authorities, the sponsor's procedures, or GCP guidelines
- Inadequate recruitment of participants by the investigator
- Discontinuation of further study intervention development

At the discretion of the sponsor, all materials and supplies provided to the investigator will be returned or disposed of in compliance with local regulatory requirements upon authorization from the sponsor, upon study completion. The investigator or designated clinical site staff will notify the IRB/IEC when the study has been completed.

10.1.11. Publication Policy

The results of this study may be published or presented at scientific meetings. If this is foreseen, the investigator agrees to submit all manuscripts or abstracts to the sponsor before submission. This allows the sponsor to protect proprietary information and to provide comments.

The sponsor will comply with the requirements for publication of study results. In accordance with standard editorial and ethical practice, the sponsor will generally support publication of multicenter studies only in their entirety and not as individual site data. In this case, a coordinating investigator will be designated by mutual agreement.

Authorship will be determined by mutual agreement and in line with International Committee of Medical Journal Editors authorship requirements.

10.2. Appendix 2. Adverse Events: Definitions and Procedures for Recording, Evaluating, Follow-up, and Reporting

10.2.1. Definition of AE

AE Definition

- An AE is any untoward medical occurrence in a patient or clinical study participant, temporally associated with the use of study intervention, whether or not considered related to the study intervention.
- An AE can therefore be any unfavorable and unintended sign (including an abnormal laboratory finding), symptom, or disease (new or exacerbated) temporally associated with the use of study intervention.

Events Meeting the AE Definition

- Any abnormal laboratory test results (e.g. hematology, clinical chemistry, or urinalysis) or other safety assessments (e.g. ECG, radiological scans, vital signs measurements, eye symptom or findings), including those that worsen from baseline, **considered clinically significant** in the medical and scientific judgment of the investigator.
- Exacerbation of a chronic or intermittent pre-existing condition including either an increase in frequency and/or intensity of the condition.
- New conditions detected or diagnosed after study start even though it may have been present before the start of the study.
- Signs, symptoms, or the clinical sequelae of a suspected DDI.
- Signs, symptoms, or the clinical sequelae of a suspected overdose of either study intervention or a concomitant medication. Overdose per se will not be reported as an AE/SAE unless it is an intentional overdose taken with possible suicidal/self-harming intent. Such overdoses should be reported regardless of sequelae.

Lack of efficacy per se will not be reported as an AE or SAE. Such instances will be captured in the efficacy assessments.

Events NOT Meeting the AE Definition

- Medical or surgical procedure (e.g., endoscopy, appendectomy): the condition that leads to the procedure is the AE.
- Situations in which an untoward medical occurrence did not occur (social and/or convenience admission to a hospital).
- Anticipated day-to-day fluctuations of pre-existing disease(s) or condition(s) present or detected at the start of the study that do not worsen.

10.2.2. Definition of ADR

- “Adverse drug reaction” or “adverse reaction” means a response to a medicine in humans which is noxious and unintended and which occurs at any dose and which can also result from overdose, misuse or abuse of a medicine. The phrase “responses to a medicinal product” means that a causal relationship between a medicinal product and an adverse event is at least a reasonable possibility, i.e., the relationship cannot be ruled out.

10.2.3. Definition of SAE

If an event is not an AE per definition above, then it cannot be an SAE even if serious conditions are met.

A SAE is defined as any untoward medical occurrence that, at any dose:

- a. Results in death**
- b. Is life-threatening**

The term 'life-threatening' in the definition of 'serious' refers to an event in which the participant was at risk of death at the time of the event. It does not refer to an event, which hypothetically might have caused death, if it were more severe.

- c. Requires inpatient hospitalization or prolongation of existing hospitalization**

In general, hospitalization signifies that the participant has been detained (usually involving at least an overnight stay) at the hospital or emergency ward for observation and/or treatment that would not have been appropriate in the physician's office or outpatient setting. Complications that occur during hospitalization are AEs. If a complication prolongs hospitalization or fulfills any other serious criteria, the event is serious. When in doubt as to whether "hospitalization" occurred or was necessary, the AE should be considered serious.

Hospitalization for elective treatment of a pre-existing condition that did not worsen from baseline is not considered an AE.

- d. Results in persistent disability/incapacity**

- The term disability means a substantial disruption of a person's ability to conduct normal life functions.
- This definition is not intended to include experiences of relatively minor medical significance such as uncomplicated headache, nausea, vomiting, diarrhea, influenza, and accidental trauma (e.g. sprained ankle) which may interfere with or prevent everyday life functions but do not constitute a substantial disruption.

- e. Is a congenital anomaly/birth defect**

- f. Is a medically significant / important event or reaction:**

- Medical or scientific judgment should be exercised in deciding whether SAE reporting is appropriate in other situations such as important medical events that may not be immediately life-threatening or result in death or hospitalization but may jeopardize the participant or may require medical or surgical intervention to prevent one of the other outcomes listed in the above definition. These events should usually be considered serious.

Examples of such events include invasive or malignant cancers, intensive treatment in an emergency room or at home for allergic bronchospasm, blood dyscrasias or convulsions that do not result in hospitalization, or development of drug dependency or drug abuse.

10.2.4. Definition of Serious Adverse Drug Reaction (Serious ADR)

When an adverse event is judged to be serious and related (see Section 10.2.6.4) to an investigational product, it is referred to as Serious ADR and is subject to expedited reporting (see Section □).

10.2.5. Definition of AESI

Adverse events of special interest (AESIs) are adverse events that the sponsor wants to monitor carefully and which are subject to expedited reporting (within 24 hours) from the investigator to the Sponsor or representative following the same process and timelines than the SAEs.

In this trial the following AEs will be collected and reported as AESI:

- Anaphylactic reaction
- \geq Grade 2 intensity (severity) and/or serious AE related to increase of heart rate (HR);
- \geq Grade 2 intensity (severity) and/or serious AE related to decrease of SBP;
- \geq Grade 2 intensity (severity) and/or serious AE related to decrease of DBP;
- \geq Grade 2 intensity (severity) and/or serious eye symptom-related AE.

10.2.6. Recording and Follow-up of AEs and SAEs

10.2.6.1. AE and SAE Recording

- Care will be taken not to introduce bias when detecting AE and SAE. Open-ended and non-leading verbal questioning of the participant is the preferred method to inquire about AE occurrences.
- When an AE/SAE occurs, it is the responsibility of the investigator to review all documentation (e.g., hospital progress notes, laboratory reports, and diagnostics reports) related to the event.
- The investigator will then record all relevant AE/SAE information in the CRF.
- AE will be reported on the AE CRF using a recognized medical term or diagnosis that accurately reflects the event.
- AE evaluations will be reviewed by the principal investigator or a medically qualified delegate. AE CRF pages are to be completed by members of the study team designated in writing by the principal investigator. The onset and resolution dates of an AE and action taken in response to the AE will be documented.
- After the initial AE/SAE report, the investigator is required to proactively follow each participant at subsequent visits/contacts. All SAE and non-serious AESI will be followed until resolution, stabilization, the event is otherwise explained, or the participant is lost to follow-up.
- It is **not** acceptable for the investigator to send photocopies of the participant's medical records to the sponsor in lieu of completion of the AE/SAE CRF page.
- There may be instances when copies of medical records for certain cases are requested by the medical monitor, the IDMC or the sponsor. In this case, all participant identifiers, with the exception of the participant number, will be redacted on the copies of the medical records before submission.
- The investigator will attempt to establish a diagnosis of the event based on signs, symptoms, and/or other clinical information. Whenever possible, the diagnosis (not the individual signs/symptoms) will be documented as the AE/SAE.
- SAE will be assessed for severity and causal relationship to the study investigational medicinal product.

10.2.6.2. Follow-up of AEs and SAEs and Resolution

- The investigator is obligated to perform or arrange for the conduct of supplemental measurements and/or evaluations as medically indicated to elucidate the nature and/or causality of the AE or SAE as fully as possible. This may include additional laboratory tests or investigations, histopathological examinations, or consultation with other health care professionals.
- If a participant dies during participation in the study or during a recognized follow-up period, the investigator will provide the sponsor with a copy of any post-mortem findings including histopathology, if available.
- New or updated information will be recorded in the CRF.
- The investigator will submit any updated SAE data to the sponsor within 24 hours of receipt of the information.
- The onset and resolution dates of the event and medical care taken in response to the event will be documented.
- AEs will be considered resolved when the condition returns to normal or returns to the participant's baseline status as established during the Screening Phase, or when the condition has stabilized with the expectation that it will remain chronic
- If the event has not resolved by the final study visit, it will be documented as "ongoing" on the eCRF, however, follow-up of the SAE must continue until resolved or the condition has stabilized. Information recorded on the CRF must be substantiated in the source documents.
- The resolution date to be recorded on the CRF is the last date on which the participant experienced the AE.

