Assess the impact on heart rate, blood pressure and ECG profile of each dose regimen of TBA-7371 and of HRZE over the 14-day treatment period.	
From Day 1 through Day 15:
 
 Mean and frequency distribution of changes in heart rate (HR), systolic blood pressure (SBP) and diastolic blood pressure (DBP) as measured by the following 2 (BP) or 3 (HR) methods: 
 manual (vital signs), after at least 10 minutes in supine position (“manual, supine”);

Objectives	Endpoints
	
 ▪ manual, after 2 (± 0.5) minutes in standing position (“manual, 2-min standing”); ▪ HR from ECG, supine position (“ECG, supine”) • Frequency of participants with $\ge 25\%$ increase in HR, decrease in SBP, decrease in DBP vs. baseline as measured with any of the methods described above. • Mean and frequency distribution of percentage of days with $\ge 25\%$ increase in HR, decrease in SBP, decrease in DBP vs. baseline. • Mean/median change from screening through Day 15 in PR, RR, QRS, QT, QTcF values from baseline ECG.
Assess whether there is tachyphylaxis over the 14-day treatment period for HR, SBP, DBP and eye symptoms.	
 • Mean change in HR, SBP and DBP from Day 1 to Days 4, 7, 10, 14 and 15 for each of the measurement methods described above. • Change in frequency of participants with eye symptoms (all, severe, serious) and change in mean visual acuity score and frequency of color vision abnormalities (tritan, protan, deutan) in one or both eyes and degree of severity (mild, moderate, and severe) from Day 1 to Days 4, 7, 10, 14 and 15.
Assess whether cardiovascular and/or ophthalmic AEs persist or recur up to 4 weeks after discontinuation of treatment with TBA-7371.	
 • Mean change in HR, SBP and DBP from screening to Days 28 and 42 and from Day 14 to Days 28 and 42 for each of the measurement methods described above. • Change in frequency of participants with eye symptoms (all, severe, serious) and change in mean visual acuity score and frequency of color vision abnormalities (tritan, protan, deutan) in one or both eyes and degree of severity (mild, moderate, and severe) from screening to Days 28 and 42 and from Days 1-15 (combined) to Days 28-42 (combined).

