Assess the impact on heart rate, blood pressure and ECG profile of each dose regimen of TBA-7371 and of HRZE over the 14-day treatment period.	
From Day 1 through Day 15:
 
 Mean and frequency distribution of changes in HR, SBP and DBP as measured by the following 2 (BP) or 3 (HR) methods: 
 manual (vital signs), after at least 10 minutes in supine position (“manual, supine”); manual, after 2 (± 0.5) minutes in standing position (“manual, 2-min standing”); HR from ECG, supine position (“ECG, supine”) Frequency of participants with $\ge 25\%$ increase in HR, decrease in SBP, decrease in DBP vs. baseline as measured with any of the methods described above. Mean and frequency distribution of percentage of days with $\ge 25\%$ increase in HR, decrease in SBP, decrease in DBP vs. baseline. Mean/median change from screening through Day 15 in PR, RR, QRS, QT, QTcF values from baseline ECG.
Assess whether there is tachyphylaxis over the 14-day treatment period for HR, SBP, DBP and eye symptoms.	
 Mean change in HR, SBP and DBP from Day 1 to Days 4, 7, 10, 14 and 15 for each of the measurement methods described above. Change in frequency of participants with eye symptoms (all, severe, serious) and change in mean visual acuity score and frequency of color vision changes from Day 1 to Days 4, 7, 10, 14 and 15.
Assess whether cardiovascular and/or ophthalmic adverse events persist or recur up to 4 weeks after discontinuation of treatment with TBA-7371.	
 Mean change in HR, SBP and DBP from screening to Days 28 and 42 and from Day 14 to Days 28 and 42 for each of the measurement methods described above. Change in frequency of participants with eye symptoms (all, severe, serious) and change in mean visual acuity score and frequency of

Objectives	Endpoints
	color vision changes from screening to Days 28 and 42 and from Days 1-15 (combined) to Days 28-42 (combined).
Assess whether there are meaningful changes in safety laboratory measurement	For each blood/serum and urine parameter: 
 • Mean, median, highest and lowest value. • Shift tables from screening to Day 3, Day 7, Day 14 and Day 42.
Secondary, PK and PK/PD	

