10.2.6.6. Assessment of SAE Outcome

The outcome of each SAE must be reported to the sponsor, even if this extends beyond the SAE reporting period (i.e. after the final study visit).

For analysis purposes, the outcome for SAE will be determined on the final study visit.

Outcome of all AE will be classified as one of the following:

- Resolved
- Resolved with sequelae
- Ongoing
- Death

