12.2 Eye Symptoms

Analysis of eye symptom-related AEs for all eye symptoms, severe eye symptoms, and serious eye symptoms will be based on new events that occurred after Screening. Severe eye symptoms are events that are assigned with grade 3 intensity or greater.

The frequency distribution of participants who experienced 1, 2, or ≥ 3 eye symptom-related AEs in one or both eyes during Day 1 to Day 15 will be summarized by treatment group for all eye symptoms, severe eye symptoms, and serious eye symptoms. The frequency and proportion (expressed in percent) of participants and 95% CI for proportions will be provided for the summary. For computing proportions, the denominator is the number of participants in the Safety population for the given treatment group.

Additionally, the frequency of symptom-related AEs and frequency and proportion (expressed in percent) of participants with eye symptom-related AEs in one or both eyes will be provided by PT and by treatment group for the following:

- All eye symptoms
- Severe eye symptoms
- Serious eye symptoms
- The frequency and proportion of participants with eye symptom-related AEs in one or both eyes that observed at Days 1, 4, 7, 10, 14, 15, Days 1-15 combined (i.e. any eye symptom-related AE observed on any Days 1-15), 28, 42, and Days 28-42 combined (i.e.

any eye symptom-related AE observed on any Days 28-42) will be provided by treatment group for the following: All eye symptoms

- Severe eye symptoms
- Serious eye symptoms

For the by-time point summary, the denominator for the proportion is the number of participants with eye symptom assessment at the given time point.

Any day that a participant reported an eye symptom-related AE in one or both eyes after screening will be counted toward the number of days of having eye symptoms in the study for that individual. Number of days of having eye symptoms will be summarized by treatment group using descriptive statistics for the following:

- All eye symptoms
- Severe eye symptoms
- Serious eye symptoms

Additionally, categorical number of days of having eye symptoms for participants with these events will be summarized by treatment group as follows:

- 1-3 days
- 4-6 days
- 7-9 days
- 10-12 days
- 13-15 days
- ≥ 16 days

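### Protocol 10.2.6.2 counts a stable, chronic adverse event as resolved, which can misstate AE outcome and, where AE dates are used, the eye-symptom persistence and duration results of SAP 12.2

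*Protocol*

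**What the plan says.** Protocol 10.2.6.2 gives three routes to a resolved adverse event: return to normal, return to the status established at screening, "or when the condition has stabilized with the expectation that it will remain chronic". Two further rules in the same list depend on that definition:

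- On events still open at the end: "If the event has not resolved by the final study visit, it will be documented as" ongoing. For SAEs, follow-up then continues until the event has resolved or stabilized.
- On dates: "The resolution date to be recorded on the CRF is the last date on which the participant experienced the AE".

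Protocol 10.2.6.1 sets the end of follow-up: "All SAE and non-serious AESI will be followed until resolution, stabilization, the event is otherwise explained, or the participant is lost to follow-up". Protocol 10.2.6.6 offers four outcomes: resolved, "Resolved with sequelae", ongoing and death. It also fixes the SAE outcome used for analysis at the final study visit.

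A secondary objective in Protocol 3.2 reads: "Assess whether cardiovascular and/or ophthalmic adverse events persist or recur up to 4 weeks after discontinuation of treatment with TBA-7371". SAP 12.2 carries out the eye-symptom part in terms of eye symptom-related AEs. It gives proportions at each visit, including Day 28, Day 42 and the two combined ("any eye symptom-related AE observed on any Days 28-42"), the number of days with symptoms, and the average duration in hours. SAP 12.1 lists the resolution date and outcome of each AE.

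**The concern.** The third route closes the events that have not gone away. Under the literal rule, a participant left with a stable, lasting eye effect has a resolved AE, and the ongoing category no longer applies because it is reserved for events that have not resolved. The trial has an objective about persistence after the drug stops, and that is the wrong direction in which to misclassify.

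At stake are the outcome field for AEs and SAEs and the listing that shows it. Also at stake are those parts of SAP 12.2 that need to know whether, and until when, an eye-symptom AE was present.

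**Working it through.** The plan states no figure on this point, so the check sets the rules side by side and then follows them into the analyses.

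1. **Resolution rule against date rule (both Protocol 10.2.6.2).** An event closed as stable and chronic is still being experienced, so it has no last day of experience. Its status is resolved, yet no valid resolution date exists. A site can satisfy one rule or the other, not both. If the end date is left blank, SAP Appendix 2 does not help: it imputes partial AE end dates but has no rule for one that is wholly missing.

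2. **Resolution rule against follow-up rules (Protocol 10.2.6.1 and the next item of 10.2.6.2).** Both name resolution and stabilization as separate reasons to end follow-up. The resolution rule makes the second a case of the first.

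3. **Resolution rule against outcome categories (Protocol 10.2.6.6).** A stable residual deficit could be entered as resolved or as resolved with sequelae. The rule does not say which, and it points away from ongoing.

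4. **Which persistence results use AE status:**
   - Heart rate and blood pressure at Days 28 and 42: measured (SAP 12.5.2, and ECG heart rate in 12.6.2). AE status is not an input.
   - Visual acuity: measured (SAP 12.3). Not an input.
   - Color vision: tested (SAP 12.4). Not an input.
   - Eye-symptom proportions, days and durations: worded in terms of AEs (SAP 12.2). Exposed if taken from AE dates.
   - AE outcome and resolution date: listed (SAP 12.1). Exposed.

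5. **Source of the SAP 12.2 data.** The form in Protocol 10.5.2 asks at Days 15, 28 and 42 about present symptoms and symptoms since the last check, with start time, whether still ongoing, and duration if over. SAP 12.2 does not say whether an AE counted at Day 28 or 42 comes from that form or from AE start and stop dates. Scheduled eye assessments after screening fall on Days 1, 4, 7, 10, 14, 15, 28 and 42, which is eight, while the day categories run to 16 or more. The day count therefore needs onset and end information for days between visits, whichever record supplies it.

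6. **Size for the Day 28 and 42 proportions.** The inputs are 15 participants per TBA-7371 regimen (Protocol 9.2) and a denominator of those with an eye symptom assessment at the visit (SAP 12.2).
   - AE dates used, and the event closed before the visit: 1/15 = 0.067, so 6.7 percentage points are lost per affected participant when all 15 are assessed. With fewer assessed the step is larger; for example, 15 − 2 = 13 gives 1/13 = 7.7 points.
   - Visit form used: 0, because the symptom is elicited again at the visit.

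**The case against.** The strongest reply is that this is a wording slip in a recording appendix with little reach. Most of the persistence endpoint is measured directly. Eye symptoms are asked about again at Days 28 and 42 whatever the earlier AE status, and symptoms the investigator considers clinically meaningful must be recorded as AEs (Protocol 8.3.7). The visit denominator in SAP 12.2 suggests visit assessments rather than AE dates. The SAP's AE tables do not tabulate outcome; it appears only in a listing. A with-sequelae category is already available, and eye symptoms in the earlier healthy-volunteer study were all transient (Protocol 4.2), so few participants may be affected.

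Much of this stands, and it rules out two stronger readings:

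- A reader might infer that a lasting cardiovascular effect would be hidden from the persistence analysis. The documents do not support that. The cardiovascular endpoint is measured heart rate and blood pressure; for cardiovascular AEs only the outcome, dates and listing are exposed.
- A reader might infer that an eye symptom starting on Day 4 and judged chronic on Day 15 would be recorded as lasting 11 days (11 × 24 = 264 h) and be absent at Days 28 and 42, when by Day 42 it had lasted 38 days (38 × 24 = 912 h). That needs a Day 15 stop date, which the date rule in 10.2.6.2 does not allow for a symptom still experienced. Absence at the visits also assumes that SAP 12.2 works from AE dates.

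The reply does not remove the contradiction. The outcome of a persisting event is misdirected whichever source SAP 12.2 uses, the SAE outcome for analysis is fixed at the final visit, and the silence of SAP 12.2 on its source is a gap in its own right.

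**Conclusion.** The point holds in a limited form. Protocol 10.2.6.2 states a rule that classes a persisting AE as resolved, against its own date rule and against the separate treatment of stabilization beside it.

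The certain consequence is an unreliable AE or SAE outcome for stable, lasting effects. The conditional one concerns eye-symptom days, durations and Day 28 and 42 counts. For the counts, the size per affected participant runs from 0 (visit form) to 6.7 percentage points (AE dates, 15 assessed, event closed before the visit). The documents do not settle where in that range the analysis falls, and they give no basis for the number of participants affected. It is worth correcting because the objective concerns persistence and the correction is small.

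**What to change.** In Protocol 10.2.6.2, confine resolved to return to normal or to screening status. Record an event that has stabilized but persists as ongoing, or as resolved with sequelae where the acute event is over and a deficit remains, and enter no resolution date while the participant still experiences it. Keep stabilization only as a reason to end active follow-up. Bring the CRF completion guidance into line.

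In SAP 12.2, state that eye-symptom status at Days 28 and 42 comes from that visit's eye symptom form, and that the duration of an event still present is counted to the last assessment and flagged as ongoing.

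The cost is one sentence in the appendix, matching CRF guidance and a short addition to SAP 12.2. The downside is that more events will be shown as ongoing at Day 42. The change concerns recording and analysis only.
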